#### Olaparib dose reductions to manage adverse events

Initial Dose	Following re-challenge post interruption: Dose reduction 1	Dose reduction 2
300 mg twice daily (2 x 150 mg tablets)	250 mg twice daily (1 x 100 mg + 1 x 150 mg tablets)	200 mg twice daily (2 x 100 mg tablets)

### 7.2 Management of hematological toxicity

Hematologic toxicity will be defined using specific AML/MDS criteria: For patients with documenting response, any CTCAE grade 4 ANC or platelet toxicity lasting >42 days from the initiation of the cycle will be considered a DLT.

In the absence of active disease, study drug should be interrupted until recovery of the hematologic toxicity to  $\leq$  Grade 3 for all subjects regardless of baseline cytopenia. The treatment will then be re-started at the lower dose level as indicated on section 7.1 of the protocol.

The definition and management of hematologic toxicities is complex and we strongly encourage the local investigator to contact the study team to discuss the next steps of management if a hematologic toxicity is suspected.

Note that a complete response with inadequate platelet recovery will not considered a hematologic toxicity.

### Olaparib dose reductions to manage hematological toxicities

Initial Dose	Dose reduction 1	Dose reduction 2
300 mg twice daily (2 x 150 mg tablets)	250 mg twice daily (1 x 100 mg + 1 x 150 mg tablets)	200 mg twice daily (2 x 100 mg tablets)

### 7.3 Management of non-hematological toxicity

Repeat dose interruptions are allowed as required, for a maximum of 2 weeks of treatment interruption total. If the interruption is any longer than this the study monitor must be informed. Where toxicity reoccurs following re-challenge with study treatment, and where further dose interruptions are considered inadequate for management of toxicity, then the patient should be considered for dose reduction or must permanently discontinue study treatment.

Study treatment can be dose reduced to 250 mg twice daily as a first step and to 200 mg twice daily as a second step. Treatment must be interrupted if any NCI-CTCAE Grade 3 or 4 AE occurs which the investigator considers to be at least possibly related to administration of study treatment, excluding febrile neutropenias and neutropenic infections.

#### 7.3.1 Management of new or worsening pulmonary symptom

If new or worsening pulmonary symptoms (*e.g.*, dyspnea) or radiological abnormalities occur in the absence of a clear diagnosis, notably consideration for lung infection, an interruption in study treatment dosing is recommended and further diagnostic workup (including a high resolution computed tomography [CT scan]) should be performed to exclude pneumonitis.

Following investigation, if no evidence of abnormality is observed on CT imaging and symptoms resolve, then study treatment can be restarted, if deemed appropriate by the investigator. If significant pulmonary abnormalities are identified, these need to be discussed with the Study Physician.

#### 7.3.2 Management of nausea and vomiting

Events of nausea and vomiting are known to be associated with olaparib treatment. These events are generally mild to moderate (CTCAE Grade 1 or 2) severity, intermittent and manageable on continued treatment. The first onset generally occurs in the first month of treatment for nausea and within the first 6 months of treatment for vomiting. For nausea, the incidence generally plateaus at around 9 months, and for vomiting at around 6 to 7 months.

No routine prophylactic anti-emetic treatment is required at the start of study treatment, however, patients should receive appropriate anti-emetic treatment at the first onset of nausea or vomiting and as required thereafter, in accordance with local treatment practice guidelines. Alternatively, olaparib tablets can be taken with a light meal/snack (*i.e.*, 2 pieces of toast or a couple of biscuits).

As per international guidance on anti-emetic use in cancer patients (ESMO, NCCN), generally a single agent anti-emetic should be considered *e.g.*, dopamine receptor antagonist, antihistamines.

#### 7.4 Interruptions for intercurrent non-toxicity related events

Study treatment dose interruption for conditions other than toxicity resolution should be kept as short as possible. If a patient cannot restart study treatment within 4 weeks for resolution of intercurrent conditions not related to disease progression or toxicity, the case should be discussed with the study physician.

All dose reductions and interruptions (including any missed doses), and the reasons for the reductions/interruptions are to be recorded in the eCRF.

Study treatment should be stopped at least 3 days prior to planned surgery. After surgery study treatment can be restarted when the wound has healed. No stoppage of study treatment is required for any needle biopsy procedure.

Study treatment should be discontinued for a minimum of 3 days before a patient undergoes radiation treatment. Study treatment should be restarted within 4 weeks as long as any bone marrow toxicity has recovered.

Because the AEs related to olaparib may include asthenia, fatigue and dizziness, patients should be advised to use caution while driving or using machinery if these symptoms occur.

#### **Olaparib dose reductions for non-toxicity related events**

Initial Dose	Following re-challenge post interruption: Dose reduction 1	Dose reduction 2
300 mg twice daily (2 x 150 mg tablets)	250 mg twice daily (1 x 100 mg + 1 x 150 mg tablets)	200 mg twice daily (2 x 100 mg tablets)

#### 7.5 Renal Impairment

If after study entry and while still on study therapy, a patient's estimated CrCl falls below the threshold for study inclusion (>30 ml/min), retesting should be performed promptly.

A dose reduction is recommended for patients who develop moderate renal impairment (calculated creatinine clearance by Cockcroft-Gault equation or based on a 24-hour urine test of between 30 and 50 ml/min) for any reason during the course of the study: the dose of olaparib should be reduced to 200 mg twice daily.

Because the CrCl determination is only an estimate of renal function, in instances where the CrCl falls to between 31 and 50 mL/min, the investigator should use his or her discretion in determining whether a dose change, or discontinuation of therapy is warranted.

Olaparib has not been studied in patients with severe renal impairment (CrCl ≤ 30 mL/min) or end-stage renal disease; if patients develop severe impairment or end stage disease it is recommended that olaparib be discontinued.

## 7.6 Dose Reductions when Receiving Strong/Moderate CYP3A4 Inhibitors

As noted in Section 6.2.3, patients should avoid taking strong or moderate CYP3A4 inhibitors while receiving olaparib. The use of any such agent must be discussed with the study monitor. If there is no suitable alternative concomitant medication, the dose of olaparib should be reduced for the period of concomitant administration. The dose reduction of olaparib should be recorded in the case report form (CRF) with the reason documented as concomitant CYP3A inhibitor use.

### Olaparib dose reductions if patient must take a strong or moderate CYP3A inhibitor

Initial Dose	Dose if Receiving a Strong CYP3A inhibitor	Dose if Receiving a Moderate CYP3A inhibitor
300 mg twice daily (2 x 150 mg tablets)	100 mg twice daily (1 x 100 mg tablets)	150 mg twice daily (1 x 150 mg tablets)

## 8. PHARMACEUTICAL INFORMATION

A list of the AEs and potential risks associated with the investigational agent administered in this study can be found in Section 10.1.

### 8.1 Olaparib (AZD2281) (NSC 747856)

**Chemical Name:** 4-[(3-{[4-(cyclopropylcarbonyl)piperazin-1-yl]carbonyl}-4-fluorophenyl)methyl]phthalazin-1(2H)-one

**Other Names:** AZD2281; KU-0059436; CO-CE 42

**Classification:** PARP inhibitor

**CAS Registry Number:** 763113-22-0

**Molecular Formula:** C24H23FN4O3

**M.W.:** 434.46

**Approximate Solubility:** 0.1 mg/mL pH independent solubility across physiologic range

**Mode of Action:** Olaparib is an inhibitor of subclasses 1, 2, and 3 of polyadenosine 5' diphosphoribose polymerase (PARP-1, PARP-2, and PARP-3). In tumors that are deficient in the homologous recombination DNA repair pathway (example, BRCA mutants), inhibition of PARP by olaparib causes accumulation of DNA double-strand breaks and genomic instability. Olaparib may also enhance the effects of DNA damage caused by ionizing radiation and chemotherapy.

**Description:** crystalline solid

**How Supplied:** AstraZeneca supplies and the Pharmaceutical Management Branch (PMB), CTEP, Division of Cancer Treatment and Diagnosis (DCTD) distributes olaparib as green, film-coated tablets in 100 mg and 150 mg strengths.

- 100 mg tablets are 14.5 mm x 7.25 mm oval-shaped
- 150 mg are 14.5 mm x 7.25 mm oval-shaped

Tablets are packaged in induction-sealed high-density polyethylene (HDPE) bottles with child-resistant closures. Each bottle contains 32 tablets with desiccant.

Tablet core components include active drug substance, copovidone, colloidal silicon dioxide, mannitol and sodium stearyl fumarate. Film coating contains hydroxypropyl methylcellulose (hypromellose), macrogol 400 (polyethylene glycol 400), titanium dioxide, iron oxide yellow and iron oxide black.

**Storage:** Store in a secure location below 30° C (86° F).

If a storage temperature excursion is identified, promptly return olaparib (AZD2281) to room temperature and quarantine the supplies. Provide a detailed report of the excursion (including documentation of temperature monitoring and duration of the excursion) to [[contact]](mailto:[contact]) for determination of suitability.

**Stability:** Shelf-life studies are ongoing. Sites are not permitted to re-package tablets. Once the bottle is opened, olaparib tablets must be used within 3 months of the opening date; unused tablets should be discarded. Instruct patients not to open a bottle until they are ready to use it.

**Route and Method of Administration:** Oral. Take tablets without regard to meals.

**Potential Drug Interactions:** *In vivo* data indicate that CYP3A4/5 is important for olaparib metabolism and clearance in humans. For this reason, avoid concomitant administration of strong and moderate CYP 3A4/5 inducers and inhibitors. Consult the protocol document or study investigator prior to making any dose adjustments related to potential drug-drug interactions.

*In vitro* data shows olaparib is a substrate for P-glycoprotein (P-gp), but not for organic anion-transporting polypeptides (OATP1B1 and OATP1B3), organic cation transporter 1 (OCT1), multi-drug resistance protein 2 (MRP-2) efflux transporter or breast cancer resistance protein (BCRP). Administration of strong P-gp inhibitors and inducers should be avoided with concurrent olaparib.

Based on *in vitro* data, olaparib inhibits CYP 3A4 and UGT1A1 enzyme systems and induces CYP 1A2, 2B6, and 3A4. Therefore, avoid concomitant administration of sensitive substrates, particularly those with narrow therapeutic ranges.

Olaparib is also an inhibitor of P-gp, OATP1B1, OCT1, OCT2, OAT3, multi-drug and toxin extrusion proteins (MATE1 and MATE2K) and a weak inhibitor of BRCP, but not an inhibitor of OATP1B3 or MRP-2. *In vitro* studies suggest that olaparib may increase exposure of substrates of these transport systems, although the clinical relevance is not clear. The manufacturer recommends that statins, in particular, should be administered with caution when given concomitantly with olaparib.

**Patient Care Implications:** Pre-clinical data indicate that olaparib adversely affects embryofetal survival and development. Therefore, women of child-bearing potential and their partners should agree to use two (2) highly effective forms of contraception starting at signing of the informed consent, throughout study participation and for at least one (1) month after the last dose of olaparib. It is not known whether olaparib is found in seminal fluid, so as a precaution, male study participants must use a condom during treatment and for three (3) months after the last dose and should avoid fathering a child or donating sperm during this same time period. The study investigator should discuss the most appropriate forms of highly effective contraceptive methods for each patient.

Lactation is a protocol exclusion criterion and not advised since there is potential for serious adverse reactions in breastfed infants. Advise lactating women to not breastfeed during study treatment and for one (1) month after receiving the last dose of olaparib.

Because the adverse events related to olaparib may include asthenia, fatigue and dizziness, patients should be advised to use caution while driving or using machinery.

There are no data on the effect of olaparib on wound healing, therefore as a precaution, olaparib treatment should be stopped at least 3 days prior to planned surgery. After surgery olaparib can be restarted when the wound has healed. No stoppage of olaparib is required for any needle biopsy procedure.

Study treatment should be discontinued for a minimum of 3 days before a patient undergoes therapeutic or palliative radiation treatment. Study treatment should be restarted within 4 weeks as long as any bone marrow toxicity has recovered.

## Availability

Olaparib (AZD2281) is an investigational agent supplied to investigators by the DCTD, NCI.

Olaparib (AZD2281) is provided to NCI under a Collaborative Agreement between the Pharmaceutical Collaborator and DCTD, NCI (see Section 13.5).

- Agent Ordering and Agent Accountability

NCI-supplied agents may be requested by eligible participating Investigators (or their authorized designee) at each participating institution. The CTEP-assigned protocol number must be used for ordering all CTEP-supplied investigational agents. The eligible participating investigators at each participating institution must be registered with CTEP, DCTD through an annual

submission of FDA Form 1572 (Statement of Investigator), NCI Biosketch, Agent Shipment Form, and Financial Disclosure Form (FDF). If there are several participating investigators at one institution, CTEP-supplied investigational agents for the study should be ordered under the name of one lead participating investigator at that institution.

Submit agent requests through the PMB Online Agent Order Processing (OAOP) application. Access to OAOP requires the establishment of a CTEP Identity and Access Management (IAM) account and the maintenance of an “active” account status, a “current” password, and active person registration status. For questions about drug orders, transfers, returns, or accountability, call or email PMB any time. Refer to the PMB’s website for specific policies and guidelines related to agent management.

Starter supplies will not be provided. Patients must be registered prior to agent ordering. Sites may request expedited orders Monday-Thursday when they provide courier information.

- Agent Inventory Records

The investigator, or a responsible party designated by the investigator, must maintain a careful record of the receipt, dispensing and final disposition of all agents received from the PMB using the appropriate NCI Investigational Agent (Drug) Accountability Record (DARF) available on the CTEP forms page. Store and maintain separate NCI Investigational Agent Accountability Records for each agent, strength, formulation and ordering investigator on this protocol.

- Investigator Brochure Availability

## 9. STATISTICAL CONSIDERATIONS

### 9.1 Study Design/Endpoints

#### 9.1.1 Study Design

This is an open-label study of olaparib in advanced relapsed or refractory IDH1/2-mutant AML and MDS. The study will have 4 arms. Arm 1 will include patients with relapsed or refractory AML with no prior exposure to IDH inhibitors (inhibitor naïve). Arm 2 will be composed of patients with relapsed or refractory AML with prior exposure to IDH inhibitors. Arm 3 will include patients with relapsed or refractory MDS with no prior exposure to IDH inhibitors (inhibitor naïve). Arm 4 will be composed of patients relapsed or refractory MDS with prior exposure to IDH inhibitors.

The effect of PARP inhibitors is dependent on 2-HG levels, and 2-HG levels are high in both IDH inhibitor naïve patients, as well as in patients who relapse after IDH inhibitors. While 2-HG levels are suppressed in patients actively on IDH inhibitors (independent of response, which discourages concomitant administration), in patients who relapse after IDH inhibitors 2-HG levels are seen to increase despite continued IDH inhibitor therapy. This has been seen in numerous studies (*e.g.*, Intlekofer *et al.*, 2018). Therefore, we expect a rather similar efficacy of PARP inhibitors in both IDH inhibitor naïve and IDH inhibitor pre-treated patients.

For the null hypothesis, the CR rate is 30% in IDH inhibitor naïve AML patient, not for patients with previous IDHi exposure. For the MDS, population, the data for IDHi naïve patients are still limited and we will have a conservative estimate that the rate of response will be similar to AML. The null hypothesis for patients already treated with at least 1 line of therapy and an IDH inhibitor will be set at 5% given the absence of available options for either MDS or AML. Sample sizes and futility rules:

Cohort	H0	H1	Alpha 1 sided	beta	Sample size stage 1	Futility	Sample size total*	Efficacy
AML IDHi naïve	30	50	5	20	19	6 or less	39	17 or more
AML IDHi exposed	5	35	5	10	8	0	14	3 or more
MDS IDH I naïve	30	50	5	20	19	6 or less	39	17 or more
MDS IDHi	5	35	5	20	6	0	12	3 or more

exposed								
---------	--	--	--	--	--	--	--	--

The calculations are based on a Simon 2 Stage Minimax design.

\* without the drop-out rate of 15%

The safety and efficacy will be evaluated by an independent data review committee at each critical step of the protocol. Given the patient population, we considered a potential drop-out rate of 15%. Expected monthly accrual is 3-4 patients per month, with a proposed total sample size of 94 patients, over 2 years.

Demographic information such as age and race will be tabulated. Descriptive statistics, including means, standard deviations, and ranges for continuous parameters, as well as percentages and frequencies for categorical parameters, will be presented. Adverse medical events will be tabulated. CTCAE Grade 3 and Grade 4 laboratory abnormalities will be listed.

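### In the two IDH-inhibitor-naïve arms the success bar of 17 meets both stated limits only at 39 analysed patients, and the plan neither fixes that number nor gives a bar for any other

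*Combined protocol and SAP*

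**What the plan says.** The design table in section 9.1.1 has one row per arm: null and target rates, one-sided alpha, beta, stage 1 size, futility count, total size and efficacy count. The two naïve rows are identical in content: "AML IDHi naïve 30 50 5 20 19 6 or less 39 17 or more" and "MDS IDH I naïve 30 50 5 20 19 6 or less 39 17 or more". For contrast, one exposed row reads "AML IDHi exposed 5 35 5 10 8 0 14 3 or more"; the MDS exposed arm has 6 then 12 patients, also with a bar of 3. The section states: "The calculations are based on a Simon 2 Stage Minimax design".

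The footnote to the total column reads "without the drop-out rate of 15" percent, and the text below the table adds "Given the patient population, we considered a potential drop-out rate of 15" percent. Enrolment is then given "with a proposed total sample size of 94 patients, over 2 years", a figure repeated in section 9.2.

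Section 9.6.2 makes a patient evaluable for response on finishing at least one cycle. The documents contain no replacement rule, no statement that non-evaluable patients count as non-responders, no rule limiting the analysis to a set number of evaluable patients, and no efficacy count for any other total.

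**The concern.** The efficacy count is the primary decision threshold in each arm, and a bare count has the stated error and power only at the sample size for which it was derived. The evaluable number is random, because it depends on who completes a cycle. If it comes out at 36 or 42, the plan does not say what count is success. Someone must then either apply 17 anyway or choose another bar. The trial is open-label, and section 13.1 gives the Protocol PI and the statistician access to the data at all times, so a bar chosen at that point would not be a pre-specified threshold.

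**Working it through.** **Inputs (9.1.1, naïve arms).** p0 = 0.30, p1 = 0.50; stage 1 n1 = 19, stop at 6 or fewer; total n = 39, success at 17 or more; one-sided alpha 5%, beta 20%; drop-out 15%.

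**Formula.** P(success | p) = sum over x1 = 7 to 19 of Bin(x1; 19, p) × P(X2 ≥ 17 − x1), with X2 ~ Bin(n − 19, p). Type I error uses p = 0.30 and power uses p = 0.50.

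**The plan's own figures.** At n = 39 this gives error 4.5% and power 80.4%. A search over two-stage designs returns the same minimax design (19, 6, 39, 17). The exposed arms also reproduce: 8/0 then 14/3 gives 2.9% and 90.5%; 6/0 then 12/3 gives 1.8% and 82.2%.

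**Attained n varied, stage 1 kept at 7 or more of 19.** The right-hand columns reset the bar to the smallest count with exact error of at most 5%.

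| n | Error, bar 17 | Power, bar 17 | Reset bar | Error | Power |
|---|---|---|---|---|---|
| 33 | 0.8% | 49.8% | 15 | 4.2% | 74.3% |
| 34 | 1.1% | 56.4% | 16 | 2.6% | 68.7% |
| 36 | 2.1% | 68.1% | 16 | 4.4% | 77.7% |
| 37 | 2.8% | 72.9% | 17 | 2.8% | 72.9% |
| 38 | 3.6% | 77.0% | 17 | 3.6% | 77.0% |
| 39 | 4.5% | 80.4% | 17 | 4.5% | 80.4% |
| 40 | 5.6% | 83.1% | 18 | 3.0% | 76.3% |
| 42 | 8.1% | 87.0% | 18 | 4.7% | 82.5% |
| 43 | 9.5% | 88.3% | 19 | 3.1% | 79.1% |
| 45 | 12.4% | 89.9% | 19 | 4.8% | 84.2% |
| 46 | 13.9% | 90.4% | 20 | 3.2% | 81.4% |

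With the bar at 17, only n = 39 meets both limits. Below 39 only power fails; above 39 only the error fails.

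**How often n differs from 39.** Inflating for drop-out gives 39/0.85 = 45.9, so 46 enrolled. Assume each drops out independently with probability 15%. Then exactly 39 are evaluable 16% of the time, more than 39 about 45%, and fewer about 38%. Averaged over the attained n, with 19 at stage 1 and the bar at 17, error is 5.0% and power 78.8%.

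**Exposed arms, bar 3.** Inflated sizes are 14/0.85 = 16.5, so 17, and 12/0.85 = 14.1, so 15. Error is 4.5% at 17 (AML) and 3.0% at 15 (MDS). Power falls to 84.5% at 12 of 14 (AML) and 72.9% at 10 of 12 (MDS).

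**Enrolment.** The totals sum to 39 + 14 + 39 + 12 = 104 before drop-out, and 104/0.85 = 122.4, so 123 with it. The plan enrols 94.

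**The case against.** The strongest reply is that the footnote makes 39 the number to be analysed, with drop-out covered by extra enrolment. On that reading 17 belongs to 39 and the design is coherent; the table states no wrong rule, and no section tells anyone to apply 17 at 33 or 46. This stands as a reading of the footnote. What is missing is a rule that makes the analysed number 39, or says what to do when it is not.

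Three stronger inferences are tempting, and the documents do not support them.

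- **That the naïve arms run at about 50% power** because 15% is lost from 39 (39 × 0.85 = 33). The footnote says the reverse: the loss is to be made up outside the 39. Under the 46-enrolled assumption, 33 or fewer evaluable is rare.
- **That the error rate is 13.9%.** That needs all 46 enrolled patients to be evaluable, which is zero drop-out; under the assumed 15% the probability is 0.85^46, about 0.06%. The average error is about 5.0%. With 94 planned against 104, a large over-run is also hard to fit if all four arms reach stage 2.
- **That all four arms share the defect.** With a bar of 3, the AML exposed arm meets both of its limits at 14 to 17 patients and the MDS exposed arm at 12 to 17.

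It may also be said that statisticians adjust such bars routinely. They do, but the adjustment is pre-specified only if it is written down before responses are seen.

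**Conclusion.** The point holds for the two naïve arms and should be fixed. Their only stated success threshold misses either the 5% error or the 80% power at every attained total other than 39. The miss is modest next to 39 (5.6% error at 40, 77.0% power at 38) and material a few patients away (8.1% at 42, 68.1% at 36). Averaged over plausible drop-out from 46 the design is close to its stated properties, so this is an unspecified contingency in the primary decision rule and not a miscalculated design. In the exposed arms the consequence is limited to lost power if an arm falls short.

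The figures assume exactly 19 patients analysed at stage 1. With 20 to 22 there, the same cut-offs and a total of 39, both limits still hold (error 4.7 to 4.9%, power 82 to 83%); with 18, power is 78.3%. The frequencies of over- and under-run rest on the assumed 46 enrolled and independent 15% drop-out.

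**What to change.** Amend section 9.1.1 in four respects.

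1. Define the efficacy population consistently with 9.6.2: treated or evaluable patients, and how non-evaluable patients count. The choice matters. If 39 are enrolled and the 15% who are non-evaluable count as failures, the response probability under the alternative is 0.50 × 0.85 = 0.425 and power is about 48%, so enrolment would have to rise or the power be restated.
2. State that if the analysed number differs from plan, the final bar is the smallest count with exact two-stage type I error of at most 5%, computed from the attained stage 1 and total numbers. With 19 at stage 1, the naïve-arm bars are 15 at 32–33, 16 at 34–36, 17 at 37–39, 18 at 40–42, 19 at 43–45 and 20 at 46. A rule that analyses only the first 39 patients of the defined population could replace the bars above 39; the two should not be combined.
3. State that this restores the 5% error but not always 80% power: with 19 at stage 1, power stays below 80% at 32 to 38, 40, 41 and 43 (for example 74.3% at 33, 72.9% at 37 and 76.3% at 40).
4. Reconcile the planned 94 with 104 before drop-out and 123 after it, and restate the power of any arm left short.

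The cost is a short paragraph and a small table. The price is a bar up to three responses higher if a naïve arm over-runs to 46, and some loss of power just above 39 (83.1% to 76.3% at 40) in return for keeping the error at 5%.

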## 9.3 Stratification Factors

Patients will be stratified based on prior exposure to IDH inhibitors. Both untreated and pre-treated cohorts will be evaluated independently from the statistical perspective. AML and MDS patients will also be analyzed separately.

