### 9.6.2 Evaluation of Response

All patients that finish at least 1 cycle of therapy will be considered evaluable for clinical response. Clinical efficacy (Cumulative Overall Response Rate, ORR) will be evaluated by MDS IWG 2006 criteria (Cheson *et al.*, 2006) and AML IWG 2003 criteria (Cheson *et al.*, 2003) after 6 cycles of treatment. Cumulative ORR will include CR, Cri, PR, marrow CR achieved at least at one point during these 6 cycles.

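### The stated total of 94 patients is below the 104 that the four arm designs require, before any allowance for the 15% drop-out

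*Combined protocol and SAP*

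**What the plan says.** The design table in Section 9.1.1 gives one Simon minimax design per arm. Its columns are H0 (%), H1 (%), one-sided alpha (%), beta (%), stage 1 size, futility bound, total size and efficacy cut-off. The first row reads "AML IDHi naïve 30 50 5 20 19 6 or less 39 17 or more", and the row for inhibitor-naïve MDS carries the same figures, so each of these two arms ends at 39 patients. Both arms with prior inhibitor treatment test a null of 5% against 35%. For AML, with beta of 10%, that arm has 8 patients at stage 1 and 14 in all. For MDS, with beta of 20%, it has 6 and then 12.

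A footnote says the total sizes are "without the drop-out rate of 15" per cent.

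Below the table, Section 9.1.1 repeats the 15% drop-out assumption and gives the overall size: "Expected monthly accrual is 3-4 patients per month, with a proposed total sample size of 94 patients, over 2 years". Section 9.2 repeats that sentence, and its planned-enrolment table also totals 94 (columns 32 + 30 + 17 + 15).

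On pooling, Section 9.3 says: "Both untreated and pre-treated cohorts will be evaluated independently from the statistical perspective". It adds that AML and MDS are analysed separately. On evaluability, Section 9.6.2 says: "All patients that finish at least 1 cycle of therapy will be considered evaluable for clinical response".

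**The concern.** The arms are tested separately, so a patient in one arm cannot count towards another and the four maxima must be added. They add to more than 94. A drop-out allowance can only raise the number to enrol, so it cannot explain a lower figure. Nothing in the documents calls 94 an expected size, a cap, or a figure that assumes some arm stops at stage 1.

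If enrolment is held to 94 and all four arms pass stage 1, at least one arm ends short of its final size. Its tabulated cut-off and error rates no longer describe the test carried out, and a negative result there is weaker evidence of inactivity. The 2-year accrual period is tied to the same figure.

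**Working it through.** **Inputs.** Arm designs, 15% drop-out, total of 94 and accrual of 3–4 per month over 24 months, from Sections 9.1.1 and 9.2. Separate testing, from Section 9.3.

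**1. Do the arm designs reproduce?** With stage 1 size n1, futility bound r1, final size n and cut-off c:

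P(success) = Σ over x from r1+1 to n1 of P(X1 = x) × P(X2 ≥ c − x), where X1 ~ Bin(n1, p) and X2 ~ Bin(n − n1, p).

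| Arm | n1 / n | Alpha | Power | P(pass stage 1), H0 / H1 |
|---|---|---|---|---|
| AML naïve, MDS naïve (each) | 19 / 39 | 0.0455 | 0.804 | 0.334 / 0.916 |
| AML exposed | 8 / 14 | 0.0286 | 0.905 | 0.337 / 0.968 |
| MDS exposed | 6 / 12 | 0.0179 | 0.822 | 0.265 / 0.925 |

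All meet their stated limits, and an exhaustive search returns each as the minimax design. The arm sizes are therefore right.

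**2. Does the total reproduce?**

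- Sum of maxima: 39 + 14 + 39 + 12 = 104, which is 10 more than 94.
- Enrolment that leaves 104 after 15% loss: 104 / 0.85 = 122.4, so 123. Rounded up by arm: 46 + 17 + 46 + 15 = 124. Shortfall 29–30.
- Evaluable patients from 94 enrolled: 94 × 0.85 = 79.9, about 80.

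**3. Could 94 be some other total?** With each arm either stopping at stage 1 or reaching its final size, the only possible totals are 52, 58, 64, 72, 78, 84, 92, 98 and 104. The expected total is 69.0 with H0 in every arm and 100.0 with H1 in every arm (81.2 and 117.7 after dividing by 0.85). None is 94. If one naïve arm stops and the other three continue, the need is 19 + 39 + 14 + 12 = 84 evaluable, or 84 / 0.85 = 98.8, so 99 enrolled.

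**4. How often would 94 be too few?** Multiply the stage 1 pass or stop probabilities across arms and add over the totals that exceed the limit: 98 and 104 exceed 94; 84, 92, 98 and 104 exceed 79.9. With H1 everywhere, all four arms pass with probability 0.916 × 0.968 × 0.916 × 0.925 ≈ 0.75.

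| Truth | More than 94 evaluable needed | More than 80 evaluable needed |
|---|---|---|
| H1 in every arm | 84% | 98% |
| Naïve at H1, exposed at H0 | 43% | 85% |
| Only MDS naïve at H0 | 31% | 88% |
| Naïve at H0, exposed at H1 | 11% | 51% |
| H0 in every arm | 6% | 15% |

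These count stopping for futility only.

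**5. What would a shortfall cost?** The plan does not say which arm would be cut, so this split is assumed: both exposed arms complete (14 + 12 = 26), the naïve arms share the rest equally, stage 1 stays at 19 with 6 or fewer as the futility bound, and the cut-off is reset to keep alpha at or below 5%.

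- 94 evaluable: (94 − 26) / 2 = 34 per naïve arm, cut-off 16, alpha 0.0259, power 0.687.
- 80 evaluable: (79.9 − 26) / 2 ≈ 27 per naïve arm, cut-off 13, alpha 0.0357, power 0.648.

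Both compare with a planned power of 0.804.

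**6. Accrual.** 24 months at 3–4 per month gives 72–96 patients. For 104: 104/4 to 104/3 = 26–35 months. For 123–124: 123/4 to 124/3 = about 31–41 months.

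**The case against.** The strongest reply is that 94 is only a proposed size beside an expected accrual rate. No text closes enrolment at 94, and the numbers that govern each arm are in the table. On that view harm arises only if enough arms continue and 94 is also enforced. This is fair, but the plan does not say it, and a reader of Section 9.2 alone would take 94 as the trial's size.

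Further points:

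- **Drop-out.** The plan gives neither a definition nor a formula. Multiplying by 1.15 gives 120–121, but 120 × 0.85 = 102, which does not deliver 104; dividing by 0.85 does. Equating drop-out with failure to finish one cycle is an assumption. If every treated patient counts, the gap is 10.
- **Power illustration.** Part of the loss is discreteness. With 34 patients a cut-off of 15 gives power 0.785, but alpha 0.0534, above the stated 5%.
- **False positives.** Keeping the cut-off of 17 in a short naïve arm does not inflate alpha (0.011 at 34 patients). The damage is to power.
- **Toxicity rule.** The holds in Section 9.1.3 are not in the probabilities and could reduce the numbers needed. If toxicity were checked after every patient (an assumption), a 39-patient arm would trigger a hold with probability about 0.10, 0.33 or 0.60 at true rates of 5%, 10% or 15%. A hold is not necessarily closure, so the percentages are best read as upper figures.

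None of this reconciles 94 with 104.

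**Conclusion.** The concern holds. The arm designs are correct and the overall total is not: 94 is 10 below the design maximum of 104, with no drop-out considered. With 15% drop-out taken as non-evaluable patients, it is 29–30 below the enrolment needed. The 104 rests only on the plan's own table and on separate testing of the arms. The 123–124 rests on the reading of drop-out. The probabilities rest on exact binomial stage 1 rules without toxicity holds, and the power loss on an assumed split of the shortfall. If every arm is inactive, 94 is usually enough; if the drug works as hypothesised in every arm, it usually is not.

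**What to change.** In Sections 9.1.1 and 9.2, replace 94 with wording such as: the maximum total is 104 evaluable patients (39 + 14 + 39 + 12), reached if all four arms pass stage 1; allowing for 15% drop-out, up to 124 patients (46, 17, 46 and 15) will be enrolled; at 3–4 per month, full accrual takes about 31–41 months. Rebuild the enrolment table to the new total, and say what counts as drop-out in relation to Section 9.6.2.

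Two alternatives are acceptable if stated:

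- If all treated patients enter the primary analysis, the figures are 104 treated and 26–35 months, and Section 9.6.2 must be changed to match.
- If 94 is a fixed ceiling, say so and restate each arm's size, cut-off, alpha and power under it.

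Under the recommended wording the cost is text and one table, with the arm designs unchanged. If every arm continues, the stated plan grows by 29–30 patients and about 7–17 months beyond 24. If all treated patients are counted, it grows by 10 patients and about 2–11 months.
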